Study Rationale	
Fructose consumption has dramatically increased over the past 20 years in the United States (US) and worldwide¹. High fructose intake has been shown to increase serum triglycerides, upregulate de novo lipogenesis, reduce fatty acid oxidation and decrease the clearance of very low density lipoprotein triglycerides in liver leading to nonalcoholic fatty liver disease (NAFLD)¹. Nonalcoholic fatty liver disease (NAFLD), the leading cause of chronic liver disease in the US, is characterized by fat accumulation in liver cells not caused by alcohol². A group of disorders including steatosis, nonalcoholic steatohepatitis with fibrosis and cirrhosis, NAFLD has substantially risen in prevalence over the last two decades with recent estimated prevalence being 20% among US adults and 25% in young adults (18-39 years).²
 
Although evidence has been presented for the positive relationship between fructose intake and NAFLD, the role of fructose in liver fat accumulation has been unclear. Individuals with specific genotypes seem to be more susceptible to the adverse metabolic effects of fructose. For example Hispanic children with rs738409 (GG) single nucleotide polymorphism (SNP) of patatin-like phospholipase, domain-containing 3 (PNPLA3) increased their liver fat by 23% more than CG/CC children exposed to the same amount of dietary fructose³. Similarly, adolescents with rs1260326 (TT) of glucokinase regulatory protein (GCKR) variant increased their de novo lipogenesis by 44% as compared to CC adolescents when given a sugar challenge⁴. Therefore, we hypothesize that when given the same amount of fructose individuals with specific set of genotypes will be more susceptible to increased de novo lipogenesis and liver fat accumulation than others.

Study Objective(s)	
Our goal for this study is to generate preliminary data that is needed to support an application to NIH for funding of a larger, adequately-powered study to explore whether a set of genotypes, that increase the risk for nonalcoholic fatty liver disease (NAFLD), predispose individuals to increased de novo lipogenesis (DNL) and liver fat accumulation when exposed to fructose intake.
 
Primary Objective: To determine the impact of acute and prolonged exposure of fructose on hepatic lipid accumulation in adolescents and young adults (12-40 years) with high and low genetic risk for NAFLD using liver mass resonance imaging (MRI).
 
Secondary Objective: To explore the genetic-specific effects of fructose on markers of liver fat accumulation (fibroscan⁵ and fatty liver index⁶) and serum biomarkers related to lipids, uric acid and liver function.

Test Article(s) (If Applicable)	Sugar-Sweetened beverages
Study Design	
 a. We will screen 200 Caucasian children and young adults (12-40 years) to obtain 24 children and 24 young adults who are overweight/obese and drink <14 fructose drinks/week to participate in a 3-week fructose intervention study. The 200 participants will be genotyped for 10 SNPs involved in lipid metabolism and associated with increased NAFLD risk in previously published studies^{7,8}. We will select 12 children and young adults with 15 or more risk alleles and 12 children and 12 young adults with 6 or fewer risk alleles and provide them fructose + glucose⁹ drinks who will ingest one drink (equal to 2 soft drinks) per day for 3 weeks; b. We will measure liver fat using Liver MRI^{9,10} and transient elastography (Fibroscan)⁵ at week 0 and 3;

c. Data will be analyzed using paired and unpaired students T test to differentiate the responses between the time points and between the two groups, respectively.

Specific Aim2: Determine the impact of acute exposure of fructose on hepatic *de novo* lipogenesis

- Using the cohort described in Specific Aim1, we will conduct oral fructose tolerance test at week 0 and week 3;
- We will measure liver fat using Fibroscan
- Data will be analyzed using unpaired students T test and repeated measures ANOVA to differentiate the responses between and within the two groups, respectively.

Specific Aim3: Determine the relationship between markers of DNL, liver fat accumulation and serum concentrations of lipids, uric acid and liver function markers before and after the fructose challenge

- We will measure serum concentrations of liver function markers, lipids and uric acid at week 0 and week 3;
- As in previous aims, data will be analyzed using students T test, and Pearsons correlations.

Subject Population	Inclusion Criteria
key criteria for Inclusion and Exclusion:	
 Subjects between 12 and 40 years No history of alcohol abuse (> 7 drinks per week) History of fructose intake of < 14 drinks per week Caucasian ethnicity BMI > 25kg/m² – 32kg/m² or 85th -99th percentile but otherwise healthy
	Exclusion Criteria
	
 ages < 12 and > 40 years Pregnant/lactating known alcohol abuse or fructose intake > 14 drinks per week not of Caucasian ethnicity glucose levels > 100 mg/dl if fasting, > 140mg/dl if within 2 hours post meal and > 200 mg/dl if random sample taking anti-hypertensive, anti-diabetic, uric acid and/or lipid-lowering medications known diagnosis of diabetes, fructose intolerance, chronic kidney disease, NAFLD or any liver-related disease, hypertriglyceridemia, polycystic ovary syndrome, hypothyroidism, obstructive sleep apnea, hypopituitarism and hypogandism BMI < 25kg/m² or > 32 kg/m² or < 85th or > 99th percentile Liver fat fraction >5% as per baseline MRI scan
Number Of Subjects	200 for first phase and 48 for the second and third phases
Study Duration	The first phase will be about 30 minutes and the second and third phase will be divided into two visits. Both visits in both phases will be about 3.5 hours each.
Study Phases	(1) Screening: We will screen participants for eligibility to participate in the study based on the inclusionary/exclusionary criteria specified above. The 200 children and young adults selected to participate will provide saliva which will be used to extract DNA and then genotype 10 SNPs. These SNPs are selected based on their association with de novo lipogenesis (DNL) or liver fat accumulation in previously published studies in Caucasians. We will select 12 children and 12 young adults with more than 15 risk alleles and 12 children and 12 young adults with less than six number of risk alleles.
Screening	
Study Treatment	
Follow-Up	
	(2) Intervention: This part is divided into two phases. Each phase entails two visits. Phase2-visit 1: The 48 enrolled (24 in each of the high and low genetic risk group) will

visit the UNC NRI clinical suite run by the Human Research Core. They will be taken to the WakeForest imaging center for their baseline MRS scan.

Visit 2: Acute fructose challenge: The next day, they will have their initial anthropometrics and Fibroscan measurements. They will then undergo an oral fructose challenge using a protocol used by Hudgins et al¹³. The participants will be provided with a drink consisting of fructose (0.75g/kg body weight) + glucose (0.45g/kg body weight) dissolved in 24 Oz of water (equal to 2 soda cans) to be consumed within 15 minutes. Blood and urine will be sampled at baseline and 1 and 3 hours after sugar drink ingestion. During the challenge period, no other beverage (except water) or food will be allowed.

3-week intervention: The 48 participants will be provided with sugar drinks for the three week period. The drinks that need to be taken per day will contain fructose (0.75g/kg body weight) + glucose (0.45g/kg body weight) dissolved in 24 Oz of water (equal to 2 soda cans) which is similar to that provided during the acute fructose challenge⁷.

[figure not shown]
Addition of glucose to fructose in the challenge and 3-week intervention induces the lipogenic effects of fructose, alleviates gastrointestinal effects of fructose and mimics the real-life situation¹⁴. They will visit at the end of each week to collect drinks for the next week. In addition, participants will be given standardized meals for the day prior to the baseline fructose challenge. They will also be instructed to avoid alcohol, juices and sodas the previous evening.

Efficacy Evaluations	Changes in liver fat accumulation through MRI scans and fibroscan measurements, and serum concentration of other lipids, liver function markers and uric acid.
Pharmacokinetic Evaluations	N/A
Safety Evaluations	
At screening, to check for blood glucose values, we will conduct a spot glucose check using a glucometer (Accu-Chek, Roche Diagnostics, CH) to check that the glucose levels of the participants are in the normal range (fasting < 100mg/dl, post meal < 140 mg/dl and random < 200 mg/dl). Secondly, we will have a physician who will be available if needed. We will also conduct pregnancy test if needed.
 
Also, we will exclude participants for further participation if we find that the participant has high liver fat fraction (>5%) during our baseline MRI scan¹⁰. The participant will be given a report that they can show to their physician for treatment.

Statistical And Analytic Plan	Our main outcome measure is change in liver fat via MRI scan, fatty liver index equation and through fibroscan measurements. We will also measure serum concentrations of other lipids, liver function markers and uric acid. Data will be assessed using descriptive measures and confidence intervals. Paired t-tests and repeated measures regression analysis will be performed to explore the significant differences between week 0 and week 3.
DATA AND SAFETY MONITORING PLAN	A data and safety monitoring plan will be instituted for this study that will ensure adherence to the protocol approved by UNC IRB. [name] (PI) and co-investigators will review the phenotype and genotype data as they are generated. Any adverse event that is reported to either the principal investigator or her designated research associates by the subject or medical staff caring for the subject and which meets the criteria will be documented as such. Any event that is reported will then generate an adverse event report, which will be submitted to the IRB. The report will include a description of the event, when and how it was reported, as well as any official chart records or documentation to corroborate the event or the reporting of the event

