Dietary factors spur the development of NAFLD: Unhealthy diet plays a major role in the development of NAFLD. Most of the attention has been on increased calorie intake. However, an important but underappreciated dietary change in US society for the past few decades has been increase in fructose intake. Contained in soft drinks, fruit juices and energy drinks, fructose affects many metabolic processes, foremost being an increase in fat accumulation in liver and contributing to the onset and progression of NAFLD (**Figure 1**). Fructose, which is almost entirely metabolized in liver, is rapidly phosphorylated to fructose 1 phosphate by fructokinase (ketohexokinase) with ATP depletion in parallel. The fructose 1 phosphate gets metabolized to dihydroxyacetone-phosphate and glyceraldehyde and finally to triglycerides¹⁵⁻¹⁷ which gets deposited in liver and leads to NAFLD.

Fructose is a more potent stimulator of DNL than glucose: In population studies, it has been shown that fructose, and not glucose, is associated with increased visceral adiposity, insulin resistance and hyperuricemia¹⁸⁻²⁰. Fructose is unique in its effects that it stimulates KHK and thus potentiates its own metabolism. Secondly, the rate of phosphorylation of fructose by KHK is 10 times higher than the phosphorylation of glucose by glucokinase. Third, fructose is directly absorbed into portal vein and delivered to liver without entering the systemic circulation. Liver, thus, is exposed to a much higher fructose load than rest of the tissues. Fourth, fructose activates the lipogenic transcriptional factors, SREBP1c and ChREBP in the liver, promoting DNL²¹. And finally, fructose tends to deplete liver ATP levels and one of the outcomes is generation of more AMP which get converted to uric acid. Uric acid has been shown to stimulate fat synthesis in the hepatocyte thus pointing to an additional pathway through which fructose can increase liver fat^{22,23}.

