1.3 Non-Clinical and Clinical Study Findings

There are no immediate benefits. In long-term, we can provide genetic risk-guided diet plans to individuals who may be at high risk.

Risks: We don't anticipate major risk since we will exclude individuals who are diabetic, pre-diabetic, have high liver fat at baseline and are at high risk for these and other metabolic diseases. The only risk can be weight gain. We will advise on cutting calories elsewhere in their daily diet. We will also advise the participants to avoid fruit juices and other sodas for the duration of 3 weeks.

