2 STUDY OBJECTIVE

2.1 Our goal for this study is to generate preliminary data that is needed to support an application to NIH for funding of a larger, adequately-powered study to explore whether a set of genotypes, that increase the risk for nonalcoholic fatty liver disease (NAFLD), predispose individuals to increased *de novo* lipogenesis (DNL) and liver fat accumulation when exposed to fructose intake.

2.2 Primary Objective: To explore the genetic-specific effects of fructose on liver fat accumulation using MRI

2.3 Secondary Objective: To explore the genetic-specific effects of fructose on markers of liver fat accumulation (fibroscan⁵ and fatty liver index⁶) and serum biomarkers related to lipids, uric acid and liver function.

3 INVESTIGATIONAL PLAN (brief overview)

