3.2 Allocation to Treatment Groups and Blinding (if applicable)

- We will allocate participants to high and low genetic risk groups

3.3

Study Duration, Enrollment and Number of Subjects

- The study has three phases. First phase will have 200 participants who will visit Human Research Core clinical suite and spend about 30 minutes providing saliva sample and completing a brief questionnaire.
- Second and third phases will have 48 participants. They will first undergo a MRI scan and next day a 3 hour acute fructose challenge (total time 3.5 hours) and then will consume sugar drink as given to them. They will visit again at the end of week 3 for further biomarker, MRI scan and fibroscan measurements.

3.4

Study Population

- Inclusion criteria: Caucasian children and young adults, overweight/obese, ages between 12 and 40 years and no history of alcohol abuse (> 7 drinks per week for a year) and no history of excessive fructose intake (> 14 drinks per week for a year). We will conduct a spot glucose check using a glucometer (Accu-Chek, Roche Diagnostics, CH) to check that the glucose levels of the participants are in the normal range (fasting < 100mg/dl, post meal < 140 mg/dl and random < 200 mg/dl).
- Exclusion criteria includes ages < 12 and > 40 years, healthy weight or morbidly obese, known alcohol abuse, not of Caucasian ethnicity, pregnancy, lactation, glucose levels > 100 mg/dl if fasting, > 140mg/dl if within 2 hours post meal and > 200 mg/dl if random, baseline MRI scan of liver fat fraction > 5%²⁷, and known diagnosis of diabetes, fructose intolerance and chronic kidney disease, use of lipid or uric acid lowering medications.

4

STUDY PROCEDURES (what will be done)

4.1

Screening/Baseline Visit procedures

Phase 1: Recruitment and screening of participants:

Screening: We will recruit 200 Caucasian children and young adults fulfilling our inclusionary criteria: ages between 12 and 40 years, overweight or obese, no history of fructose intake > 14 drinks per week and alcohol abuse (> 7 drinks per week for a year). Height will be measured to the nearest 0.1 cm by a stadiometer situated against the wall in an upright standing position. Height and weight recorded will be used to calculate BMI as kg/m². We will match all participants for BMI (25kg/m² -32kg/m² or 85th-99th percentile).

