6.4 Sample Size and Power

Although our sample of 48 may not have the power to detect significant effects of fructose on liver fat, this group of 48 well-characterized individuals, focusing only on one ethnicity and one body weight group and specific genotypes will reduce variability and will generate meaningful data. We expect to apply these approaches and use these data to estimate sample size for larger studies with significant power to detect the effects of gene-nutrients interactions on NAFLD and other metabolic disorders.

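### With one common fructose + glucose drink, dietary advice and no comparator, the all-participant week 0 to week 3 change cannot be attributed to fructose; the genetic-risk contrast can be estimated only as a difference in response to the whole regimen

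*Combined protocol and SAP*

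**What the plan says.** **Objectives.** The synopsis (Study Objective(s)) gives the primary objective as "To determine the impact of acute and prolonged exposure of fructose on hepatic lipid accumulation". The same sentence goes on to name the two genetic-risk groups and the liver scan as the measure. Specific Aim 2 uses the same verb for acute fructose exposure and de novo lipogenesis. Section 2.2 is narrower: "Primary Objective: To explore the genetic-specific effects of fructose on liver fat accumulation using MRI".

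**Intervention.** The synopsis says: "The 48 participants will be provided with sugar drinks for the three week period". Each daily drink "will contain fructose (0.75g/kg body weight) + glucose (0.45g/kg body weight"). Sections 1.2 and 7 repeat this composition for everyone.

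**Groups.** Section 3.2 gives the only allocation: "We will allocate participants to high and low genetic risk groups".

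**Advice.** Section 1.3 says: "We will advise on cutting calories elsewhere in their daily diet". It also tells participants to keep off fruit juice and other sodas for the three weeks. Section 4.2 (Dietary guidance) sets the reduction at about 500 kcal a day.

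**Analysis.** For liver fat, section 6.3 names paired t-tests and repeated-measures regression between week 0 and week 3. It adds a regression on area under the curve for the acute challenge. The unpaired comparison of the two genetic groups appears in the synopsis (Study Design), not in 6.3. Section 6.4 says the sample "may not have the power to detect significant effects of fructose on liver fat".

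**The concern.** An objective that speaks of the impact of fructose needs something in the design that varies fructose while glucose, energy and advice stay fixed. Nothing here does. All participants get one drink with one fixed sugar ratio and the same advice, and they differ by design only in genetic score and age group.

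The plan does not treat the two sugars as interchangeable. Section 1 has a paragraph headed "Fructose is a more potent stimulator of DNL than glucose", and the synopsis says the added glucose brings out the lipogenic action of fructose. Fructose is therefore not a neutral label for the drink.

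What is at stake is the wording of the conclusion. A rise in liver fat over three weeks could be read as a fructose effect. A flat result could be read as no fructose effect when the dietary advice had offset the drink.

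**Working it through.** **Inputs from the documents.** Fructose 0.75 g/kg and glucose 0.45 g/kg per drink, one drink a day (synopsis, 1.2, 7). Worked example at 65 kg (4.2). Advised cut of about 500 kcal a day (4.2). Habitual intake under 14 fructose drinks a week at entry, and a study drink equal to two soft drinks a day (synopsis). 48 participants, 24 per genetic group (synopsis).

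**Assumed, because the documents give no figure.** 4 kcal per gram of sugar; two-sided alpha 0.05; 80% power; the drift sizes in step 5.

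1. *The plan's own dose figures.* 65 × 0.75 = 48.75 g fructose and 65 × 0.45 = 29.25 g glucose. Both match section 4.2. The glucose share is 0.45/(0.75 + 0.45) = 37.5%, the same at every body weight.

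2. *Net energy.* 48.75 + 29.25 = 78 g, and 78 × 4 = 312 kcal (293 at 3.75 kcal/g). Full adherence to the advised cut gives 312 − 500 = −188 kcal a day at 65 kg. At 50 kg it is 240 − 500 = −260, and at 100 kg it is 480 − 500 = −20. With no adherence the net change is the full energy of the drink. The sign of the net energy change is thus not fixed by the design. The 500 kcal figure and the worked dose also need reconciling.

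3. *Net sugary drinks.* The study drink equals 2 × 7 = 14 soft drinks a week. Someone just under the entry limit who gives up all habitual drinks adds almost nothing, and someone with no habitual intake adds the full amount.

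4. *What each contrast estimates.* Write the mean change in a group as F + G + E + A + T: fructose, glucose (with its interaction with fructose), net energy, other effects of advice, and time.
   - All participants: one observed change and five unknown terms. With 0 of 48 on another drink or in a control period, F cannot be separated at any sample size.
   - High minus low risk: any term equal in both groups cancels. What remains is the sum of the group differences in F, G, E, A and T. This can be estimated, but it is a difference in response to the regimen, not to fructose alone.

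5. *What an uncontrolled paired test would do.* With a non-fructose change of d standard deviations (SD) and no fructose effect, the test statistic is noncentral t with n − 1 degrees of freedom and noncentrality d√n.

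| Assumed drift d | Rejection rate, n = 24 | Rejection rate, n = 48 |
|---|---|---|
| 0 | 5% | 5% |
| 0.2 | 16% | 27% |
| 0.3 | 29% | 53% |
| 0.5 | 65% | 92% |

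These rates illustrate the problem. They are not an estimate of the drift in this trial.

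6. *Is an added arm feasible at 48?* The genetic contrast at 24 v 24 can detect about 0.83 SD of change. Splitting the 48 into genotype × drink cells of 12 leaves the interaction detectable only at (1.96 + 0.84) × √(4/12) ≈ 1.62 SD. Detecting a 0.83 SD interaction needs about 47 per cell, or 4 × 47 = 188. At this size, narrowing the claim is the practical repair.

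**The case against.** The strongest reply is that the question is genetic. The quoted objective goes on to name high and low genetic risk, the hypothesis in the synopsis (Study Rationale) is that genotypes respond differently to the same amount of fructose, and 2.2 says the same. A common drink is what that comparison needs. This stands. A reader might infer that the primary objective as a whole cannot be met, and the documents do not support that. Only the all-participant reading fails, together with the attribution of the group difference to fructose alone.

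The glucose is disclosed and justified, in part as closer to real life. That supports the choice of drink. It does not license assigning the response to one ingredient.

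The study is a declared exploratory pilot, and 6.3 contains no rule for attributing the change. It is therefore a prediction, not a planned step, that a rise would be reported as a fructose effect. This lowers the severity. It does not settle the point, because the objective's own wording makes the attribution, and 6.4 concedes power, which is a different matter.

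A reader might also infer that the larger study would be built on a fructose main effect. Section 6.4 describes its target as gene-nutrient interactions, so this does not follow.

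Nor should it be inferred from the presence of *GCKR* in the score that a group difference would be a glucose response. It is one of ten variants, and the finding cited in section 1 came from a combined fructose and glucose challenge.

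Diet recalls and body weight are collected, so net energy change can be described. They cannot separate the two sugars of the drink, whose ratio is the same for everyone.

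**Conclusion.** The point holds in this form. The all-participant week 0 to week 3 change cannot be attributed to fructose, because 37.5% of the sugar is glucose, everyone receives the same advice, and none of the 48 has a comparator drink or control period. The synopsis primary objective, Aim 2 and 6.4 are worded more strongly than that, and 6.3 leaves the contrast the study can estimate unnamed for liver fat. The high versus low genetic-risk difference remains estimable as a difference in response to the common regimen. The groups are formed by genotype and not randomised, so it is an association.

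This should be changed before analysis, but it does not undermine the pilot. The identification argument needs no assumed numbers. It rests on reading the text as describing no comparator; one figure is not shown, but nothing in the text points to one. The energy, drift and detectable-difference figures depend on the assumptions stated with them.

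**What to change.** Without adding an arm or changing the intervention:

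1. Restate the synopsis primary objective, 2.2 and 6.4 as the difference between high and low genetic risk in the three-week change in liver fat, under a daily fructose + glucose drink given with dietary advice. The acute part of the synopsis objective then sits under Aim 2.
2. Restate Aim 2 separately as the acute response to a single fructose + glucose challenge drink, compared between genetic-risk groups. The regimen wording in item 1 must not be used here: the week 0 challenge is one drink taken before the daily drinks begin (section 7).
3. In 6.3, name the between-group difference in change, already in the synopsis, as the main contrast for liver fat. State that the all-participant week 0 to week 3 change is descriptive and will not be attributed to fructose.

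The cost is protocol and SAP wording, and a narrower claim: the study will report how two genetic groups differ in response to a regimen, not what fructose does.

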Genes and gene by nutrient interactions play a major role in the regulation of NAFLD: Both genetic and environmental factors contribute to the onset and progression of NAFLD. NAFLD is a complex and heritable phenotype. Family-based studies have reported heritability estimates for NAFLD to be between 20% and 70%^{7,8}. Genome-wide and candidate gene studies have identified several genes associated with NAFLD⁸. Representative genes that were implicated in lipid metabolism and in the development and progression of NAFLD are shown in **Table1**. Few studies have shown that fructose affects lipogenesis in liver in a genotype-specific manner. Davis and colleagues found that Hispanic children with GG genotypes of *PNPLA3* SNP rs738409 were more inclined to accumulate fat in the liver as compared to children with CC or CG genotypes³. Similarly, another study investigating the effects of added sugars on liver fat found that individuals with TT of rs1260326 of *GCKR* increased their *de novo* lipogenesis by 44% during an oral fructose + glucose challenge⁴. However, none of the studies have shown the cumulative effects of SNPs on change in liver fat when exposed to fructose.

The genetic-specific effects of fructose on liver lipogenesis need to be studied as a first step towards individualized nutrition: This study assumes significance given that fructose affects liver lipogenesis differentially based on genotypes. It also paves the way towards individualized or personalized nutrition. Previous studies investigating the metabolic effects of fructose have been controversial. Some have shown significant effects of fructose on insulin sensitivity and *de novo* lipogenesis and triglycerides while others have shown no effects²³⁻²⁷. The range of these studies is wide, with the duration of the intervention ranging from 7 to 665 days, sample size ranging between 8 and 64 per group and amount of fructose per day ranging from 40 to 250g/d. For this exploratory and feasibility study we have selected the duration of 21 days, sample size as 12 per group and amount of fructose a ~0.75g/kg/day (equivalent to two sodas/per day).

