6.3 Statistical Methods

Each subject will be given sugar drink containing fructose and liver MRI scan with fibroscan measurements will be taken at baseline and end of 3 weeks. Data will be assessed using descriptive measures and confidence intervals. Paired t-tests and repeated measures regression analysis will be performed to explore the significant differences between week 0 and week 3. Also, for each subject, the area under the curve (AUC)¹³ will be computed and a linear regression with AUC as the response will be performed during the acute challenge.

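### The high-versus-low t tests ignore the 12 + 12 age quota inside each risk group; if response differs by age, their intervals are wider than they need to be

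*Combined protocol and SAP*

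**What the plan says.** Age group is built into the sample. In the synopsis, under Study Phases (Screening), the plan is to select "12 children and 12 young adults with more than 15 risk alleles and 12 children and 12 young adults with less than six" risk alleles. The Intervention paragraph confirms the group size: "24 in each of the high and low genetic risk group". The Study Design entry gives the age totals, aiming "to obtain 24 children and 24 young adults who are overweight/obese".

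The analysis does not refer to this structure.

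- **Aim 1** (synopsis, Study Design, item c): "paired and unpaired students T test to differentiate the responses between the time points and between the two groups, respectively".
- **Aim 2** (synopsis): an unpaired t test between the two groups and repeated measures ANOVA within them.
- **Aim 3** (synopsis): t tests and Pearson correlations, without saying whether the t tests are paired or unpaired.
- **Section 6.3**: paired t tests and a repeated-measures regression for week 0 against week 3. For the challenge test, "a linear regression with AUC as the response will be performed during the acute challenge". No predictors are listed for either regression.
- **Section 4.5**: concomitant medication is to enter the analysis as a covariate. No other covariate is named anywhere.

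Section 1 gives the size as "sample size as 12 per group". Section 6.4 offers no power calculation. It concedes that 48 may be too few and says the data will be used to size larger studies.

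**The concern.** Filling both risk groups with the same numbers of children and young adults makes age group a balanced factor, orthogonal to risk group. Balance takes age out of the difference in means, but it does not take age out of the SD that a plain t test uses. The within-group SD of 24 people still contains the spread between the two age halves. The test then reports a larger standard error than the design delivers, its interval covers more than 95%, and its type I error falls below the nominal level.

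Two things are at stake. The first is precision in a sample fixed at 48, which Section 6.4 already describes as possibly underpowered. The second is the SD carried forward: if the planning SD for the larger study came from this t test, it would include the age difference.

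**Working it through.** **Plan's own figures.** 2 risk groups × 2 age groups × 12 = 48, and 2 × 12 = 24 per risk group. These agree with the synopsis. There is no power calculation to reproduce, because no alpha, power, effect size or SD is stated.

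**Inputs.** Four cells of 12 (synopsis). Assumptions, not in the documents: a common within-cell SD σ, a difference of d × σ between children and young adults in the analysed response, the same d in both risk groups, and a two-sided 5% level.

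**Variance used by the t test.** Within a group of 24, each age half lies dσ/2 from the group mean. This adds 24 × (d/2)² = 6d² (in units of σ²) to the expected sum of squares, which is divided by 23. Expected pooled variance = σ²(1 + 6d²/23), on 46 df.

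**Variance used by a model with risk group + age group.** σ², on 45 df. With balanced cells the high-minus-low estimate is the same in both analyses, and its true standard error is σ√(1/24 + 1/24) = 0.289σ.

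**Interval-width ratio (t test / adjusted).** t(0.975, 46) × √(1 + 6d²/23) / t(0.975, 45), with t values 2.0129 and 2.0141. For d = 0.5: 6 × 0.25/23 = 0.065, √1.065 = 1.032, and 1.032 × 2.0129/2.0141 = 1.031.

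A simulation (40,000 trials per value of d, normal errors) adds the type I error, and the power for an assumed risk-group difference of 0.8σ:

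| d (assumed) | Variance inflation | Width ratio | Type I error, t test | Type I error, adjusted | Power, t test | Power, adjusted |
|---|---|---|---|---|---|---|
| 0 | 1.000 | 0.999 | 5.0% | 4.9% | 77% | 77% |
| 0.2 | 1.010 | 1.005 | 4.9% | 5.0% | 77% | 77% |
| 0.5 | 1.065 | 1.031 | 4.3% | 5.0% | 76% | 78% |
| 0.8 | 1.167 | 1.080 | 3.4% | 4.9% | 72% | 78% |
| 1.0 | 1.261 | 1.122 | 2.9% | 5.0% | 69% | 77% |

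The lost degree of freedom is repaid once d exceeds √{[(2.0141/2.0129)² − 1] × 23/6}, which is about 0.07.

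**Which d applies.** The Statistical and Analytic Plan entry in the synopsis speaks of change in liver fat; Section 6.1 speaks of liver fat estimation. On a change score, a constant age difference in level cancels, and d is the age difference in the three-week change only. On week 3 values, the difference in level counts as well.

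**The case against.** The best counter-argument is that d may be close to zero. The outcome is probably a change, the drink is dosed by body weight, BMI is restricted, and people with high baseline liver fat are excluded. All of this narrows age differences in response. The error is also conservative, the estimate is unbiased, and the study calls itself exploratory. All of that stands. It limits the size of the point but does not remove it, since the adjusted model loses nothing visible even at d = 0. Nor does it show that d is zero: the fatty liver index, listed with the main outcomes in Section 6.1, uses absolute BMI and waist circumference, while eligibility runs on two BMI scales for ages 12 to 40.

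A reader might go further in four ways that the documents do not support.

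- *That the intervals are too wide as a matter of fact.* This depends on d, which is not given.
- *That the Section 6.3 regressions leave age out.* They list no predictors at all, not even risk group, so they are silent on age. The repeated-measures regression is aimed at week 0 against week 3, and Section 4.5 shows that covariates are foreseen. Only the unpaired t tests clearly have no age term.
- *That "sample size as 12 per group" shows the age cells were forgotten.* With 48 participants, 12 fits only as one risk-by-age cell, so the phrase is consistent with the cells and says nothing about the analysis.
- *That the larger study will be mis-sized.* The documents do not say which SD will be used. With 45 df, a 95% interval for an SD runs from about 0.83 to 1.26 times the estimate, so an SD inflation of 3% (d = 0.5) or 8% (d = 0.8) lies well inside the sampling error.

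**Conclusion.** The point holds as a conditional one. The design balances age group within risk group, and the unpaired t tests of Aims 1 and 2 make no use of it. If the analysed response differs by age, the high-versus-low interval is wider than necessary: 0.5% at d = 0.2, 3% at 0.5, 8% at 0.8, 12% at 1.0, and no visible change at d = 0. For an assumed 0.8σ effect, the power lost is about 2 points at d = 0.5 and 8 points at d = 1.0.

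These figures rest on equal within-cell SDs, the same age difference in both risk groups, and cells that stay at 12. Exclusion at the baseline MRI or withdrawal could unbalance the cells, and the estimate would then no longer be protected from an age difference. This is a worthwhile and almost free gain in precision; the planned test is not invalid.

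**What to change.** - In synopsis Study Design item c and in Aim 2, replace the unpaired t test with a linear model of the week 0 to week 3 change on risk group plus age group (child / young adult). Report the high-minus-low difference with its 95% CI.
- Report the within-cell residual SD from that model for planning the larger study, with a note that it applies if that study also adjusts for age.
- In Section 6.3, name the predictors of the regressions. Wherever they compare risk groups, include the same age-group term.
- In Section 1, restate the size as 24 per risk group, 12 per age cell. This is for consistency only.

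The cost is a few lines of text, one model term and one degree of freedom (45 instead of 46). No extra participants or measurements are needed.
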